Preventing and Limiting Adverse Events

We will monitor for risk of using e-cigarettes and NRT by screening participants for general medical precautions. The most likely adverse event (potential for nicotine overdose) is anticipated to be rare and mild based on the PI's previous studies, and will be handled quickly (i.e., advice to participant to reduce or eliminate nicotine use). Lab studies of toxin exposure suggest that e-cigarettes incur no greater risk to health than do combustible cigarettes. The PI and study personnel will be available for any questions that participants may have about e-cigarettes, NRT, smoking, or smoking cessation. Participants will be provided a study phone and data plan at no cost, to contact study personnel at any time. Any adverse events, breaks of confidentiality, or any other data or safety issues that arise will be discussed immediately between study personnel and the PI.

Collection of Adverse Events

The collection of adverse events will be on a self-report basis and logged within an electronic data capture system (REDCap) or collected using standardized paper forms and will only be identified with the study's ID of the participant.

Adverse Event Reporting Timelines

- All intervention staff are required to notify the PI of any Serious Adverse Events immediately.
- All Serious Adverse Events will be reported immediately to the medical monitor who will determine their severity and appropriate action or response.
- In accordance with current standard procedure, the PI will notify the OSU IRB of all Serious Adverse Events within 24 hours.
- In accordance with new policy and procedure, the PI will notify the National Institutes of Drug Abuse of all Serious Adverse Events within 72 hours.
- All Non-serious AEs will be reviewed weekly by the medical monitor or PI, for categorization and possible action.

Switching to a Vaping Device: Evaluating Risk Reduction among Quitline Treatment Failures

I. Literature Cited

1. CDC. Vital Signs: Current Cigarette Smoking Among Adults Aged \geq 18 Years—United States, 2005–2010. In: MMWR, ed.2011.
2. Treating tobacco use and dependence: 2008 update. Clinical Practice Guidline. 2008. at [http://www.ahrq.gov/clinic/tobacco/treating_tobacco_use08.pdf.'\).](http://www.ahrq.gov/clinic/tobacco/treating_tobacco_use08.pdf.)

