Aim 2: To evaluate changes in iCO, a biomarker of tobacco constituent exposure. *Hyp 2: The degree of change will be directly associated with the degree of substitution with J or NRT—greater levels of substitution will confer a larger decrease in exposure to harmful constituents.*

Aim 3: To evaluate which EC device characteristics and perceived effects influence complete (vs. partial or no substitution). *Hyp 3a: Participants reporting higher product satisfaction, including product durability, battery life, “throat hit”, taste, craving reduction, improved mood with use, and ease of use, will achieve higher rates of complete substitution.*

B. Significance

Quitting is Difficult for Many Smokers

Nearly 50% of smokers make a quit attempt each year, but less than 5% remain abstinent for 3-12 months after quitting.¹⁻³ As a result, the prevalence of cigarette smoking among adults in the U.S. remains disturbingly high.¹ Current cessation products and counseling are effective, doubling a smokers chances of long-term abstinence, but are not universally effective for all smokers, and most smokers fail to quit on their first attempt.⁴⁻⁷ Moreover, a significant minority of smokers finds it very difficult to quit smoking with current FDA-approved products.⁸ To prevent these individuals from returning to smoking following a failed quit-attempt, offering them other less toxic and carcinogenic forms of nicotine would potentially offer a significant health benefit over smoking. This approach is consistent with a tobacco harm reduction model, which asserts that it is preferable to reduce tobacco-related harm by having smokers switch to less toxic products when complete cessation is unobtainable⁹; electronic cigarettes maybe one such product.

The Promise of Electronic Cigarettes: Overview and Limitations of the Available Research

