enrolled in quitline treatment 4-6 months prior will be offered participation in the present study by Optum or OSU research staff. Those eligible and who agree to participate will be randomized by Optum research staff and mailed JUUL (tobacco or menthol-flavor, 5% nicotine pods) or NRT (nicotine patch plus lozenge) by OSU study staff. Both arms will also be provided three calls from Optum coaches. The Randomized Product Trial Phase (Time: 0-8 weeks) will last 8 weeks and smokers will be asked to attempt to completely switch to JUUL for the 8 week time period. All JUULs will be mailed to the participants in two shipments (Time 0, +4 weeks) by OSU study staff and provided at no cost. Those participating in the JUUL arm will also be provided three calls (~10-15 min each) from an Optum coach (Time 0, +1, +4 weeks) who will provide behavioral counseling including education on ECs, how to use and troubleshoot the EC if issues arise, and help address potential barriers to switching and develop strategies to switch. Those randomized to NRT will be provided nicotine patch plus nicotine lozenge and will also receive three behavioral counseling calls from an Optum coach. Each call will last 10-15 minutes each. The Surveillance Phase (Time: 9-12 weeks) will last 4 weeks, during which time no study product will be provided, only assessment of continued product use (or not) and other outcomes of interest (see Table 3), as well as iCO, a biomarker of toxicant exposure and effects will be measured. Over the course of the study, participants will complete a larger assessment battery at three time points: 0, +8, +12 weeks over the phone with OSU study staff. Time points for study visits are based on matching other switching studies in the literature and to fit within the short time-window of the U01. All participants will also be provided a study smartphone and a portable carbon monoxide monitor (iCO) which will be sent by OSU study staff. Participants will be asked to complete two brief (<3 minute each) daily smoking/JUUL diary assessments and iCO readings (to verify smoking status) for the 12-week duration of the study using the provided smartphone and portable iCO.

Study Weaknesses and Design Considerations

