a total of \$330. Participants will be compensated up to \$25 at Baseline, \$85 at Week 4, \$110 at Week 8 and \$110 at Week 12 study periods. Payments will be made using the Greenphire ClinCard to increase accountability and facilitate ease of payment. Participants will also be provided a study smartphone for the duration of their participation with paid service for 3 months so that they can immediately contact study staff for questions, receive reminders of upcoming appointments and study protocol, and complete EMAs and iCO tests. We will also facilitate study calls/visits by offering evening and weekend call times/appointments as well as additional retention strategies (e.g., multiple sources of contact, reminder calls/texts/emails). These methods are consistent with our team's previous studies and have resulted in excellent retention rates (>80%).^{75,87,88,90,99,100,104,105}

Detailed Study Procedures

Coach Calls: All study participants will receive three calls (~10-15 minutes) from trained tobacco cessation coaches at Time 0, +14 days, and +4 weeks. Prior to randomization, participants will complete the baseline assessment over the phone or online via REDCap. For participants randomized to JUUL, coaches will provide behavioral counseling and education on ECs, how to use and troubleshoot the JUUL device, and aid in helping the participant develop strategies to help them switch to JUUL. Coaches will also assess for JUUL usage at the +14 days and +4 week calls to help determine if the quantity of the study product that was mailed to the participant should be increased or decreased. For those randomized to NRT control, coaches will provide smoking cessation counseling grounded in social cognitive theory and the US PHS clinical guidelines. Specifically, cessation counseling will emphasize five keys to quitting tobacco: setting a quit date, using cessation medications, tobacco-proofing one's environment, coping with urges to smoke, and enlisting social support.¹⁰⁶

Baseline and Follow-up Assessments: All participants will have the baseline assessment battery (0) completed over the phone or online via REDCap with an Optum coach or OSU study team member before they are randomized to a study group; , follow-up assessments calls and mailing of JUUL pods and NRT will be conducted by [name] staff at the Ohio State University. Follow-up assessments will be conducted at +8 and +12 weeks.

Baseline Phase (Randomization)

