Immediately following the baseline assessment, participants will be randomized to one of two arms for a period of 8 weeks: JUUL or NRT. Randomization will occur using a stratified block-randomization procedure with small, random sized-blocks. Randomization will be stratified by sex, education level (high school or less, GED, or greater than GED/High School), location and EC regular use history (ever at least once weekly for a month). Consistent with our previous and ongoing switching studies^{10,75,107}, participants will be instructed on how to use the JUUL, provided a starter kit (device and a charger) as well as pods initially at a 1:1 level based on established baseline smoking rate. Given JUUL pods, if completely consumed, have been found to excrete mean total nicotine equivalents associated with consuming 91% of a pack of cigarettes. We will assume that most pack a day smokers will require no more than one pod per day. The amount provided to participants will be documented and tracked throughout the study. Provision of additional pods will be titrated up or down based on use. All products will be given to participants in their original packaging and at no cost. Consistent with previous QL studies, participants in the NRT arm will be provided patch and lozenge (2 or 4 mg); for the nicotine patch, dosing will be determined by reported cigarettes per day. Specifically, for participants smoking 5-10 cigarettes per day they will be provided with 4 weeks of the 14 mg and 4 weeks of the 7 mg nicotine

Switching to a Vaping Device: Evaluating Risk Reduction among Quitline Treatment Failures

patches; participants smoking 11+ cigarettes per day will be provided 4 weeks of 21mg, 2 weeks of 14mg, and 2 weeks of 7mg nicotine patches. All NRT will be provided for up to 8 weeks.

Randomized Product Trail Phase

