At the first visit, JUUL participants will be provided instructions on how to use the product and asked to attempt to completely switch to the product for the next 8 weeks so that we can accurately assess the use of the products on their health. Consistent with our previous EC switching studies,^{75,107} participants will be asked how they intend to completely switch to the product and asked about concerns they have about switching. Optum coaches will help participants address any reported barriers to switching to assist them in remaining switched over the 8-week period. Study staff will provide participants trouble-shooting tips for the mechanics of their product, provide replacement parts as needed, and also address adverse events as they arise (though <2% and mild in our team's previous EC studies).

Protocol Adherence and Quality Control

Data Management

Switching to a Vaping Device: Evaluating Risk Reduction among Quitline Treatment Failures

All data collection will follow HIPAA guidelines. Data will be collected directly from the participant by a research assistant or RIU coach. Data will include participant responses to computer-based, smartphone/EMA-based, and phone based survey questionnaires. All participants will be asked for an iCO sample daily for 12 weeks. A total of approximately 84 iCO samples will be collected from a single participant not to exceed 90 samples for any individual within the 12 week period.

Access to Identifiable Information and Data Storage: Only research assistants who have completed training in the ethical conduct of research and the study PI ([name]) will have access to individually identifiable private information about human subjects. All data will be treated as confidential and will never be stored or reported in association with identifying information. Participants will be consented verbally or electronically and mailed a hard copy of the consent. A common identification number will link identifiable forms (consent forms and contact information) and study-related data. Computer entered data will be de-identified and password protected.

Quality Assurance

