All participants will be mailed a study smartphone and iCO device, and provided 3 months of unlimited call and data service at no charge and will complete EMAs twice a day for all 12 weeks. Participants will receive one EMA delivered randomly during the day and an evening daily diary (~30 minutes before bedtime). Given the half-life of CO (4-12 hours), we will only request that participants complete iCO measurement for the evening daily diary. Consistent with our team's previous studies, random EMAs will assess: mood, affect, nicotine craving and withdrawal symptoms, stress, recency of vaping/smoking, alcohol use, current setting, and switching self-efficacy; daily diary EMAs will assess conventional cigarettes smoked per day, number of JUUL pods used (if applicable), cigarette/EC satisfaction and pleasure, and measurement of exhaled carbon monoxide with the iCO (see Table 2 for specific EMA measures). All EMAs will be prompted and initiated by the phone. The phone will audibly and visually cue these EMAs for 30 seconds. If the participant has not responded after 3 prompts, the assessment will be recorded as missed. Typically, random sampling assessments take ~1-2 minutes to complete and daily diary assessments take approximately ~3-4 minutes to complete. Participants will be compensated for EMA completion at the 8 and 12 week follow-ups. All assessments will be date and time stamped for future analyses. Participants have the ability to call (e.g., if they have problems completing EMA's) and receive calls from research staff through the smartphone free of charge. The EMA methodology used in this study has been successfully followed by our team as well as other researchers in multiple studies.¹¹⁹⁻¹²⁸ All participants will be sent prepaid mailing boxes and asked to return

Switching to a Vaping Device: Evaluating Risk Reduction among Quitline Treatment Failures

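### Aim 2 analyses change in iCO, but the plan schedules no reading before first product use and does not say which reading is the baseline

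*Combined protocol and SAP*

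**What the plan says.** - **The aim.** Section A makes change in iCO the subject of Aim 2. Hyp 2 reads: "The degree of change will be directly associated with the degree of substitution with J or NRT", with larger falls expected at higher substitution.
- **Baseline and randomisation.** Section D.2, Coach Calls: "Prior to randomization, participants will complete the baseline assessment over the phone or online via REDCap". Section D.2, Baseline Phase: "Immediately following the baseline assessment, participants will be randomized to one of two arms for a period of 8 weeks: JUUL or NRT".
- **Shipping.** Section D.1: "Those eligible and who agree to participate will be randomized by Optum research staff and mailed JUUL" or NRT, with the first JUUL shipment at Time 0. On the devices, the same section says: "All participants will also be provided a study smartphone and a portable carbon monoxide monitor (iCO) which will be sent by OSU study staff". Section D.3 repeats it: "All participants will be mailed a study smartphone and iCO device". Section H.1 makes one centre responsible for shipping products, phones and monitors. None of these places dates the monitor shipment or says which parcel arrives first.
- **Readings.** Section D.3: "Given the half-life of CO (4-12 hours), we will only request that participants complete iCO measurement for the evening daily diary". Section D.2, Data Management: "A total of approximately 84 iCO samples will be collected from a single participant not to exceed 90 samples for any individual". In Table 2 the iCO row is blank at baseline and marked at +8 and +12 weeks. Section D.2 places about 120 EMAs in the product phase and about 60 in the surveillance phase.
- **Analysis.** Section E.2 analyses changes in iCO by reference to the methods of another hypothesis, whose number is missing. If Hyp 1b is meant, the method is a linear mixed model that adjusts for the outcome's baseline value.

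**The concern.** An analysis of change needs a value from before the change. On the sequence described, the participant has no monitor at the remote baseline assessment. Product and monitor then travel by mail, with nothing to ensure that a reading comes first. Ticking baseline for iCO in Table 2 would not help by itself, because no monitor would be at hand to take the reading.

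If the first available reading is used as baseline, its meaning depends on when each person stopped smoking relative to that reading. Someone who has already switched starts low and stays low. Someone who never switches starts high and stays high. Both show a change near zero, although Hyp 2 puts them at opposite ends.

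There is a second problem for the arm comparison. A first reading taken after product start is a post-randomisation value that treatment may already have altered, so adjusting for it can bias the arm contrast in change. Different timing by arm is plausible: JUUL participants are asked to switch for the whole 8 weeks, while NRT counselling includes choosing a quit date.

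**Working it through.** **1. The plan's own count.** One evening reading per day for 12 weeks gives 12 × 7 = 84, which reproduces the stated figure. The cap of 90 leaves 90 − 84 = 6. The EMAs, at two per day, give 120/2 + 60/2 = 60 + 30 = 90 days, in line with the 90 days of daily assessment in Table 2. All of them are assigned to the product and surveillance phases. None is assigned to a period before product, so the gap between 84 and 90 is not a run-in.

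**2. Share of smoking CO left at the first reading.** Input: the half-life of 4-12 hours in section D.3. Formula: share left = 0.5^(hours since last smoking / half-life).

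| Smoke-free hours | Half-life 4 h | Half-life 12 h |
|---|---|---|
| 12 | 0.5^3 = 12.5% | 0.5^1 = 50% |
| 24 | 0.5^6 = 1.6% | 0.5^2 = 25% |
| 48 | 0.5^12 = 0.02% | 0.5^4 = 6% |

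**3. The fall that would be recorded.** The documents give no CO level for this population while smoking. Assume 15, 20 or 30 ppm, with a background of 2 ppm. The true fall on complete switching is the smoking level minus 2. If the first reading is the baseline, the recorded fall is that amount times the share left.

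| Assumed smoking CO | True fall | Recorded, first reading at 12 h | Recorded, first reading at 24 h |
|---|---|---|---|
| 15 ppm | 13 ppm | 1.6-6.5 ppm | 0.2-3.2 ppm |
| 20 ppm | 18 ppm | 2.2-9.0 ppm | 0.3-4.5 ppm |
| 30 ppm | 28 ppm | 3.5-14.0 ppm | 0.4-7.0 ppm |

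A reading taken before switching would record the whole fall in each row.

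**4. Effect on Hyp 2 (illustration only).** A simulation of 420 participants over 500 runs used these assumptions: smoking CO with mean 20 and SD 7 ppm (floor 7 ppm) and background 2 ppm; 27.5% complete switchers, which is the average of the planned 35% and 20%; other participants cutting exposure by 0-70%; measurement SD 2 ppm; half-life drawn between 4 and 12 hours. With a true baseline, the correlation between fall in iCO and degree of substitution was 0.79. With the first reading as baseline, it depended on the share of complete switchers who had switched 24 hours before that reading:

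| Share already switched | 0% | 25% | 50% | 75% | 100% |
|---|---|---|---|---|---|
| Correlation | 0.77 | 0.60 | 0.44 | 0.24 | 0.01 |

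**The case against.** The strongest reply is that the plan is silent here, not wrong. No text dates the monitor shipment, and the participant flow chart, which could show the order, was not readable. If monitor and product arrive together and a reading is taken that evening, the gap may be 12 hours or less and more of the signal survives. The plan also never says that the first reading is the baseline. About 84 daily values per person allow iCO level, instead of change, to be related to substitution. Eligibility requires at least 5 cigarettes per day and smoking in the past 24 hours, so smoking at entry is established, and baseline consumption is available as a rough proxy.

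Most of this stands as a limit on size. It does not supply the missing value: the schedule as written secures no CO reading before product, and none can be recovered later.

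Three stronger readings are tempting but not supported:

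- *That every first reading follows product use.* The order of arrival is not stated.
- *That the fastest switchers will show the least change.* Non-switchers also show about none, and the effect is confined to people who switch before their first reading.
- *That the Hyp 2 association would reverse.* In the illustration it falls to about zero and not below.

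**Conclusion.** The point holds as a gap in the measurement schedule and in the definition of baseline for Aim 2. With the first reading as baseline, a participant who had already switched would record 12.5-50% of the true fall if 12 hours had passed and 1.6-25% if 24 hours had passed. These shares rest on the protocol's half-life and on complete cessation over those hours. The ppm figures and the correlations rest on assumed CO levels. How many participants would be affected cannot be derived from the documents, so the attenuation could lie anywhere from negligible to nearly complete.

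A reader might infer that the trial's main result is at risk. On this ground it is not. Complete substitution uses an absolute cut-off of 6 ppm, and randomised comparisons of iCO levels at 8 and 12 weeks need no baseline. What is exposed is Hyp 2 and any baseline-adjusted analysis of change. This is a cheap improvement worth making before enrolment, not a flaw that invalidates the design.

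**What to change.** - Ask participants to complete at least one evening iCO reading and diary after the monitor arrives and before first product use, and record the date of first use.
- Define the Aim 2 baseline as the mean of these readings, and restore the missing hypothesis number in section E.2.
- For anyone without such a reading, do not use the first reading after product start as baseline. Analyse their iCO levels at 8 and 12 weeks instead of change.

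Up to 6 such readings fit under the cap (84 + 6 = 90) and within the roughly 200 tests for which the sensor is stated to be valid. If daily monitoring really runs for 90 days, as the EMA counts imply, the cap would need raising by the number of added readings; 90 + 6 = 96 is still well under 200.

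The cost is a short delay before product use for some participants and some skipped readings. No new device or procedure is needed.

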The purpose of this 8-week phase will be to assess the effect of JUUL on product uptake and use, smoking behavior, and nicotine dependence, as well as level of toxicant exposure.. During this phase, participants will receive three OKHL coaching calls (0, +14 days, +4 weeks), complete EMAs twice a day (~120 EMAs over the phase), and complete two follow-up full assessment battery calls (0 and +8 weeks). Participants randomized to JUUL will be provided EC education, behavioral counseling, and asked to attempt to completely switch to the product for the next 8 weeks. Those randomized to NRT will be provided OKHL smoking cessation counseling and provided 8 weeks of NRT. All products to which participants will be randomized, will be provided at no cost and will be mailed to them. New cartridges will be provided based on estimated use given cigarettes per day. (see Table 2 for measures collection schedule).

Surveillance Phase

The purpose of this 4-week period is to assess how EC use evolves over time; specifically, continued use as measured by reported purchase of commercial EC product, transitions to other types or styles of ECs, smoking and other tobacco use behavior and patterns, as well as continued monitoring of iCO, a biomarker of toxicant exposure, and health effects over the 4-week period. During this phase, participants will continue to complete daily EMAs (~60) and a follow-up full assessment battery call at +12 weeks. Participants will be sent saliva collection kits if iCO is unable to be completed. Participants will not be provided ECs or NRT during this phase, but use of ECs, NRT, and other tobacco products will continue to be tracked. Also, this phase will help us to continue to track any adverse events that may occur following use of the JUUL and NRT. Those continuing to use any tobacco or EC product at the end of the surveillance phase will be advised that they can contact their state quitline and/or other local smoking cessation resources.

JUUL Education and Counseling

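### Continued e-cigarette use in weeks 9-12 is measured by reported purchase, which can miss participants vaping on left-over study pods whom the daily diary would record

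*Combined protocol and SAP*

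**What the plan says.** Section A includes continued use in the overall aim of the study. Section D.1 describes weeks 9-12 as a period in which no study product is supplied and continued use is assessed. Section D.2, Surveillance Phase, gives the measure: "continued use as measured by reported purchase of commercial EC product". The same paragraph adds that "use of ECs, NRT, and other tobacco products will continue to be tracked", without saying which of the two defines continued use.

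On supply, section D.2, Baseline Phase, provides "pods initially at a 1:1 level based on established baseline smoking rate", assumes that "most pack a day smokers will require no more than one pod per day", and states that "Provision of additional pods will be titrated up or down based on use". D.1 gives two shipments, at Time 0 and +4 weeks. The Coach Calls text has coaches check use at +14 days and +4 weeks. The product trial phase text in D.2 gives a different basis for new cartridges: use estimated from cigarettes per day.

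On returns, section D.3 says "All participants will be sent prepaid mailing boxes and asked to return", and the item to be returned is the study phone. The amount of product sent out is tracked. No return or count of unused product is described.

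On use, the evening diary in D.3 records JUUL pods used, for all 12 weeks. Table 2 adds vaping sessions to the daily diary, recency of vaping to the random prompts, and a JUUL use evaluation at +12 weeks.

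**The concern.** Purchase and use are different things when participants may still hold free product. Someone vaping every day in weeks 10 and 11 on pods mailed in week 4 has bought nothing, and on the stated measure has not continued.

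The error would not be random. Under constant use, a participant who uses nearly the whole allotment runs out soon after week 8 and has to buy in order to go on, so purchase picks that person up. A participant who uses a small or moderate share can go on without buying, so purchase misses that person. The measure would therefore undercount continued use mainly among lighter users. The phase is meant to show how use evolves once free supply ends, and the protocol has no item that separates left-over stock from bought stock.

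**Working it through.** The plan states no figure for continued use, so there is none to reproduce. The check is a pod balance: can left-over stock cover weeks 9-12?

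**Inputs from the protocol**
- Initial supply 1:1 to baseline smoking, and at most about one pod a day for a pack-a-day smoker (D.2, Baseline Phase).
- Two shipments, at Time 0 and +4 weeks (D.1).
- Later supply adjusted to use (D.2, Baseline Phase), or set from cigarettes per day (D.2, product trial phase).
- Surveillance lasts 4 weeks, that is 28 days (D.1).

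**Assumptions, not in the protocol**
- 28 pods per 4-week shipment before any adjustment.
- A constant share *f* of the 1:1 allotment is used throughout.

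Use over weeks 1-8 is 56*f* pods. The need for weeks 9-12 is 28*f* pods. Left-over stock covers the phase if stock at week 8 is at least 28*f*.

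**Case 1, second shipment not adjusted.** Supply 56. Stock = 56 − 56*f*. Condition: 56 − 56*f* ≥ 28*f*, so 84*f* ≤ 56 and *f* ≤ 2/3.

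**Case 2, second shipment cut to the use rate.** Supply 28 + 28*f*. Stock = 28 + 28*f* − 56*f* = 28(1 − *f*). Condition: 28(1 − *f*) ≥ 28*f*, so *f* ≤ 1/2.

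**Case 3, second shipment cut to the use rate and net of unused pods.** Second shipment = max(0, 28*f* − 28(1 − *f*)). For *f* ≤ 1/2 this is zero and stock = 28 − 56*f*. Condition: 28 − 56*f* ≥ 28*f*, so *f* ≤ 1/3. For *f* > 1/2 the stock at week 8 is zero.

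| Share used | Need, weeks 9-12 | Stock, case 1 | Stock, case 2 | Stock, case 3 |
|---|---|---|---|---|
| 0.25 | 7 | 42 | 21 | 14 |
| 0.50 | 14 | 28 | 14 | 0 |
| 0.75 | 21 | 14 | 7 | 0 |

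At 0.25 the stock covers the phase in all three cases. At 0.50 it does so in cases 1 and 2. At 0.75 it does so in none. Because supply is 1:1, the thresholds do not depend on the baseline smoking rate.

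**Which outcomes use purchase?** Complete substitution is defined in D.3 by cigarettes smoked, exhaled carbon monoxide and reported e-cigarette use over the same seven days. Section E.2 analyses that outcome at 8 and 12 weeks. Section E contains no analysis of continued use and none by purchase.

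**The case against.** The strongest reply is that purchase is one clause in a statement of purpose, not a scoring rule, and that actual use is recorded daily. A participant vaping on left-over pods would appear as a vaper in the diary and at the +12-week evaluation. Stock at week 8 could be approximated as pods sent minus diary pods used, subject to missed diaries. All of this stands, and it limits the damage: the data for a correct classification are already planned. It does not remove the problem, because the only measure named for continued use is purchase, and Section E does not say that the diary takes precedence.

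A reader might infer several stronger points that the documents do not support.
- *The primary outcome, or the week-12 comparison under Hypothesis 1a, is biased by this measure.* It is not. The primary comparison is at week 8, before the phase begins, and complete substitution at both times uses reported use.
- *Every partial switcher can last the phase on left-over pods.* Not so. The 1:1 rule applies initially, and adjustment to use limits what remains.
- *Most participants will have pods left.* Section B reports dual use as the most common outcome, but from two trials of early devices that the protocol itself sets apart for their limited nicotine delivery. Dual use also does not say how many pods go unused.
- *Continued NRT use is misclassified in the same way.* The purchase clause concerns e-cigarettes only.

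Finally, the absence of any recovery of pods is inferred from silence in the protocol. Study staff may intend one.

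**Conclusion.** The concern holds for the descriptive measure of continued e-cigarette use. On the stated measure, a participant who vapes through weeks 9-12 on study pods and buys none is classed as not continuing. With 28 pods per shipment and constant use, this is possible for anyone using up to 1/3 to 2/3 of the allotment, depending on how the second shipment is set. The protocol does not settle which case applies, because its two statements on later supply differ. How many participants fall in that range cannot be derived from the documents.

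The classification of complete substitution at weeks 8 and 12 is unaffected. What remains for week 12 is a matter of reading: a result at that time should not be described as free of study product unless it is known that none remained. The protocol does not itself make that claim.

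**What to change.** In section D.2, Surveillance Phase, define continued e-cigarette use in weeks 9-12 as any diary-reported use (pods used or vaping sessions), and report purchase as a separate measure. This is a wording change that uses data already collected. Missed diaries and misreporting remain as sources of error.

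Two optional additions would help interpretation: one item on the source of the product (left-over study product, bought, other) and one question at the +8-week call on study product remaining. Week-12 results could then be described by whether study product remained. The cost is a small added burden on participants and one descriptive table. Both have to be asked during the trial, since supply minus diary use gives only an approximation afterwards.

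The statements on later pod supply in D.2 (adjusted to use in the Baseline Phase text, estimated from cigarettes per day in the product trial phase text) must be reconciled.
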